12.6.2 Serious Adverse Events

An SAE is any untoward medical occurrence, in the view of either the investigator or sponsor, that:

- results in death
- is life-threatening
- results in inpatient hospitalization or prolongation of existing hospitalization
- results in persistent or significant disability/incapacity
- is a congenital anomaly/birth defect

This document is confidential.

Page 64 of 85

MetrioPharm AG MP1032	MP1032-CT05	
	Final	
MetrioPharm AG	MP1032-CT05	
MP1032	Protocol v2.0	

Other important medical events that may not be immediately life-threatening or result in death or hospitalization, based upon appropriate medical judgment, are considered SAEs if they are thought to jeopardize the patient and/or require medical or surgical intervention to prevent 1 of the outcomes defining an SAE. SAEs are critically important for the identification of significant safety problems; therefore, it is important to take into account both the investigator's and the sponsor's assessment. If either the sponsor or the investigator believes that an event is serious, the event must be considered serious and evaluated by the sponsor for expedited reporting.

12.6.3 Serious Adverse Event Reporting

An SAE occurring from the time the patient gives informed consent until the end of the followup period (Day 60) or within 30 days of stopping the study drug (whichever is longer) must be reported to the Syneos Health Safety and Pharmacovigilance group and will be communicated to the sponsor. Any such SAE due to any cause, whether or not related to the study drug, must be reported within 24 hours the investigator's awareness of the event. Notification can be made using the dedicated fax line or email for the Syneos Health Safety and Pharmacovigilance group:

- Syneos Health Safety and Pharmacovigilance fax number: CCI
- Syneos Health Safety and Pharmacovigilance email address:

If the investigator contacts the Syneos Health Safety and Pharmacovigilance group by telephone, then a written report must follow within 24 hours and has to include a full description of the event and sequelae in the format detailed in the SAE reporting form.

The event must also be recorded on the standard AE eCRF. Preliminary reports of SAEs must be followed up by detailed descriptions later on. Clear and anonymized photocopies of hospital case reports, consultant reports, autopsy reports, and other documents must be provided when requested by Syneos Health Safety and Pharmacovigilance. SAE reports must be made whether or not the investigator considers the event to be related to the investigational drug.

Appropriate remedial measures should be taken to treat the SAE, and the response should be recorded. Clinical, laboratory, and diagnostic measures should be employed as needed to determine the etiology of the problem. The investigator must report all additional follow-up evaluations to the Syneos Health Safety and Pharmacovigilance group within 24 hours of becoming aware of the additional information. All SAEs will be followed up until the investigator and sponsor agree the event is satisfactorily resolved.

Any SAE that is not resolved by the end of the study or upon discontinuation of the patient's participation in the study is to be followed up, if possible, until it either resolves, stabilizes, returns to baseline values (if a baseline value is available), or is shown to not be attributable to the study drug or procedures. It is understood that if a patient withdraws consent to further follow-up, then it may not be possible for the study site to follow the SAE to resolution.

This document is confidential.

Page 65 of 85

MetrioPharm AG	MP1032-CT05
MP1032	Protocol v2.0

12.6.4 Suspected Unexpected Serious Adverse Reactions

AEs that meet all of the following criteria will be classified as suspected unexpected serious adverse reactions (SUSARs) and reported to the appropriate regulatory authorities in accordance with applicable regulatory requirements for expedited reporting:

- serious
- unexpected (ie, the event is not consistent with the reference safety information in the current version of the IB)
- there is at least a reasonable possibility that there is a causal relationship between the event and the study drug

The investigator will assess whether an event is causally related to the study drug. Syneos Health will consider the investigator's assessment and determine whether the event meets the criteria for being reportable as a 7-day or 15-day safety report. SUSARs that are fatal or life-threatening must be reported to the regulatory authorities and the IRBs/IECs (where required) within 7 days after Syneos Health/MetrioPharm has first knowledge of them, with a follow-up report (when applicable) submitted within a further 8 calendar days. Other SUSARs must be reported to the relevant regulatory authorities and the IRBs/IECs within 15 calendar days after Syneos Health/MetrioPharm first has knowledge of them.

Syneos Health is responsible for reporting SUSARs and any other events required to be reported in an expedited manner to the regulatory authorities and for informing investigators of reportable events, in compliance with applicable regulatory requirements within specific timeframes. Investigators will notify the relevant IRBs/IECs of reportable events within the applicable timeframes.

12.6.5 Pregnancy

WOCBP must have a negative serum pregnancy test at screening and negative urine pregnancy test before the first dose on Day 1. A urine pregnancy test will be repeated on Day 14 (\pm 7 days). If the patient is discharged before Day 14, urine pregnancy test at day of discharge should be done, and urine pregnancy test at Day 14 is not required. If the patient is discharged after Day 14, urine pregnancy test should be done at Day 14, and urine pregnancy test at day of discharge is not required (whichever comes first). Patients with a positive pregnancy test will be discontinued from study drug. After administration of study drug, any known cases of pregnancy in female patients will be reported until the patient completes or withdraws from the study. The pregnancy will be reported immediately by faxing/emailing a completed pregnancy report to Syneos Health Safety and Pharmacovigilance within 24 hours of knowledge of the event. The pregnancy will not be processed as an SAE; however, the investigator will follow up with the patient until completion of the pregnancy and must assess the outcome in the shortest possible time but not >30 days after completion of the pregnancy. (It is understood that if a patient withdraws consent to further follow-up, then it may not be possible for the study site to follow the pregnancy to completion.) The investigator should notify Syneos Health Safety and

This document is confidential.

Page 66 of 85

MP1032-CT05

MetrioPharm AG MP1032	MP1032-CT05	
	Final	
MetrioPharm AG	MP1032-CT05	
MP1032	Protocol v2.0	

Pharmacovigilance group of the pregnancy outcome by submitting a follow-up pregnancy report. If the outcome of the pregnancy involved spontaneous or therapeutic abortion (any congenital anomaly detected in an aborted fetus is to be documented), stillbirth, neonatal death, or congenital anomaly, the investigator will report the event by faxing/emailing a completed pregnancy report form to Syneos Health Safety and Pharmacovigilance group within 24 hours of knowledge of the event.

If the investigator becomes aware of a pregnancy occurring in the partner of a patient participating in the study, the pregnancy should be reported to Syneos Health Safety and Pharmacovigilance group within 24 hours of knowledge of the event. Information regarding the pregnancy must only be submitted after obtaining consent from the pregnant partner. The investigator will arrange counseling for the pregnant partner by a specialist to discuss the risks of continuing with the pregnancy and the possible effects on the fetus.

Upon discontinuation from the study drug, only those procedures that would not expose the patient to undue risk will be performed. The investigator should also be notified of pregnancy occurring during the study but confirmed after completion of the study. In the event, that a patient is subsequently found to be pregnant after inclusion in the study and received at least one dose of study drug, any pregnancy will be followed to term, and the status of mother and child will be reported to Syneos Health Safety and Pharmacovigilance group after delivery.

12.6.6 Overdose

The investigator must immediately notify Syneos Health of any occurrence of overdose with the study drug.

B PHARMACOKINETICS

B1 Pharmacokinetic Sampling

Blood samples for PK analysis of MP1032 plasma concentrations will be collected at the time points indicated in the Schedule of Assessments (Table 1) from a PK subset of approximately 30 patients (who give optional consent). In summary, PK samples will be collected via sparse sampling from these 30 patients (approximately) in a 2:1 ratio (approximately 20 patients from the 300 mg MP1032 BID plus SoC group and approximately 10 patients from the placebo group plus SoC group) to assess the PK of MP1032 on Day 1 (single dose) and Day 7 (steady state). A total of 16 samples (approximately 4.9 mL per time point for a total of approximately 78.4 mL) will be collected relative to the first dose on Day 1 and the first dose on Day 7. Samples on Day 1 and Day 7 will be collected predose (within 10 minutes before the first daily dose) and postdose at 10 minutes, 20 minutes, 30 minutes, 60 minutes, 120 minutes, 8 hours (before next dose), and 24 hours before the next morning dose (if applicable), if possible. Patients who provide consent for the PK sampling, but are no longer hospitalized on Day 7, will not have Day 7 PK samples collected.

This document is confidential.

Page 67 of 85

MetrioPharm AG MP1032	MP1032-CT05 Final
MP1032	Protocol v2.0

For patients in the PK subset on Day 1 and Day 7 only: Patients should not eat within the 4 hours before planned study drug administration and within the 120 minutes after study drug dosing, when feasible. Thus, study drug should be administered in fasted state (\geq 4 hours), when feasible. However, if a patient has eaten within the 4 hours before their planned administration, study drug dosing may proceed. The patient's fed or fasted state, as well as food intake (yes/no) within the 120 minutes after study drug dosing should be recorded. The PK samples should be collected as planned regardless of the patients' fasted/fed state. The study site should record the date and time of dosing (recorded as the time when the first capsule is administered).

Intravenous cannulas may be used for blood collection to avoid multiple skin punctures, when appropriate. Otherwise, blood samples will be collected by direct venipuncture. The actual date and time of each blood sample collection will be recorded. Sample collections completed outside the predefined time windows (windows to be specified in the laboratory manual) will not be considered as protocol deviations because actual postdose sampling times will be used for PK and statistical analyses.

PK samples will be analyzed by a central laboratory facility (Prolytic GmbH). Details of PK blood sample collection, processing (including separation of plasma), storage, and shipping procedures will be provided in a separate laboratory manual.

B.2 Pharmacokinetic Analytical Methodology

The concentration of study drug will be determined from the plasma samples using a validated analytical method. Details of the method validation and sample analysis will be included with the final clinical study report (CSR).

14 OTHER ASSESSMENTS

14.1 Biomarkers

Blood samples will be obtained at the visits specified in the Schedule of Assessments (Table 1) on Day 1 (before the first study drug administration) and Days 7, 14, 21, 28, and 60 (when possible) to measure biomarkers levels. Blood samples for biomarkers must be collected on Days 7, 14, 21, 28, and 60 if a patient is still hospitalized. If a patient is discharged, the study site should arrange an outpatient visit (ie, at the study site) to accommodate the collection of blood samples for biomarkers on Days 7, 14, 21, 28, and 60.

Biomarkers will potentially include, but will not be limited, to cytokines (eg, C-reactive protein, IL-1 β , IL-6, TNF- α , and IFN- γ), and other coagulation/inflammatory biomarkers (eg, D-dimer and ferritin). Samples may be collected at the same time that samples are collected for the clinical laboratory assessments. Blood samples will be analyzed by a central laboratory facility. Details of sample collection, processing, storage, shipping procedures, and analysis will be provided in a separate laboratory manual.

This document is confidential.

Page 68 of 85

MetrioPharm AG MP1032	MP1032-CT05 Final
MetrioPharm AG	MP1032-CT05
MP1032	Protocol v2 0

Please note: Patients will be requested to provide consent for the sponsor to store and use leftover blood samples for future exploratory biomarker research. Patient participation in the storage and use of leftover blood samples is optional. If the patient consents, the sponsor will store and use the leftover blood samples for a period of 3 years after the last patient has completed his/her last visit in this study.

15 STATISTICAL ANALYSIS

The statistical analysis plan (SAP) will provide further details regarding the definition of analysis variables and analysis methodology to address all study objectives. The SAP will be finalized before any statistical output (eg, DSMB output) is produced. The SAP will serve as a companion document to the protocol. The SAP will further describe the statistical analyses. All data will be included with the final CSR.

The statistical evaluation will be performed using $SAS^{(R)}$ software version 9.4 or higher (CCI \square).

Summary statistics will be presented by treatment group. Continuous and ordinal variables will be summarized by the number of patients (N), mean, standard deviation, median, minimum, and maximum for actual values and change from baseline. Additionally, for ordinal data, the number and percentage of patients in each category will be presented. Binary and categorical variables will be summarized for each treatment group by presenting the number and percentage of patients in the categories.

Statistical tests for comparison between treatments will be performed using a two-sided alpha level of 10%. No adjustment for multiple testing will be applied in this descriptive proof-of-concept study.

151 Determination of Sample Size

The primary efficacy endpoint "proportion of patients with disease progression on Day 14" is assumed to be 10% in the 300 mg MP1032 BID plus SoC treatment group (Arm A) and 30% in the placebo plus SoC treatment group (Arm B). Using the Chi-square test with type I error alpha=10% two-sided for this proof-of-concept study and 2:1 randomization ratio, with 114 randomized patients (76 in Arm A and 38 in Arm B) a statistical power of 83% can be achieved. Considering about 5% early study terminations, the necessary sample size to randomize results is 120 patients in total (80 in Arm A and 40 in Arm B). If during the conduct of the study the early study termination rate is higher than the estimated 5%, then an increase in the randomized number of patients may be necessary.

Sample size estimation was performed using nQuery 8, Version 8.6.1.0.

A subset of randomized patients will be consented for the collection of blood samples for PK measurements. The PK subset consists of approximately 20 patients from the 300 mg MP1032 BID plus SoC group and approximately 10 patients from the placebo plus SoC group, up to a total of approximately 30 patients.

This document is confidential.

Page 69 of 85

MetrioPharm AG	MP1032-CT05
MP1032	Protocol v2.0

15.2 Analysis Sets

Screened Set

The Screened Set will include all patients who give informed consent and are screened. For this group, patient disposition, and reasons for premature study termination or screening failure will be described.

Randomized Set

The Randomized Set will include all patients randomized. Unless specified otherwise, this set will be used for all subject listings with exception of the listing presenting screening failures and the respective reason(s) for screen failure.

Intention-To-Treat Set

The Intention-to-Treat (ITT) set, correspond with randomized set, will include all randomized patients irrespective of any deviation from the protocol or premature discontinuation from study drug/withdrawal from study. The treatment group assignment will be designated according to initial randomization. The ITT will serve as the basis for the analysis of efficacy and summary of demographics and baseline characteristics.

Per Protocol Set

The Per Protocol Set (PPS) will include all patients from ITT who received at least 1 dose of study drug and who do not have any major protocol deviations impacting the efficacy assessments. The PPS will be used for supportive analyses of efficacy.

Safety Set

The Safety Set (SS) will include all randomized patients who receive at least 1 dose of study drug. The treatment group assignment in the SS will be defined by the treatment actually received. The SS will be used for the analysis of safety.

PK Analysis Set

The PK Analysis Set (PKS) will include all the patients who have been administered active study drug and have at least 1 postdose evaluable plasma concentration after Day 1 dose.

15.3 Efficacy Analysis

The estimands for the primary efficacy endpoint, and for the 4 key secondary endpoints comparing the 2 treatment groups, will be tested with consideration of a two-sided type-1 error alpha of 10% for each test on the ITT. Additionally, 95% confidence intervals will be provided. Also, the treatment comparison with regards to the other secondary efficacy endpoints will be performed using a two-sided alpha level of 10%.

The main estimand for the primary efficacy endpoint is defined as follows:

This document is confidential.

Page 70 of 85

- Treatment: 300 mg MP1032 BID plus SoC in Arm A and placebo BID plus SoC in Arm B. If a patient terminates the study drug, but still remains in the study and is followed up, then the patient will continue to receive either SoC alone or SoC+ additional treatment. These treatments are defined with regards to intercurrent events as 'other treatments'.
- Population: Of all patients defined by the study inclusion/exclusion criteria, the analysis population will include patients who were randomized to study drug (ITT population).
- Variable: A binary variable indicating disease progression (death or respiratory failure) at Day 14. Respiratory failure is defined as patients who have a score of 2, 3, or 4 on the NIAID 8-point ordinal scale.
- Intercurrent events: All events that lead to study drug discontinuation and/or switch to other treatment before Day 14 will be handled using the treatment-policy strategy (ie, the NIAID score at Day 14 will be used for definition of the failure in such patients).
- Population-level summary: Common risk difference resulting from the Mantel-Haenszel (MH) test considering the 4 strata out of the combinations of the 2 randomization stratification factors disease severity (moderate versus severe) and ageclass (aged ≤65 years versus >65 years) at baseline.

Missing data on Day 14 resulting from study termination before Day 14 are not expected. However, in case they happen, such monotone missings will be imputed by multiple imputation using information from similar patients of the same treatment group. Missing postbaseline data for patients randomized but not treated will be imputed by the respective baseline value (baseline observation carried forward [BOCF]). The comparison between the treatment groups will be performed on the ITT after imputation of missing values using MH test for common risk difference considering the 4 strata resulting from the 2 randomization stratification factors disease severity (moderate versus severe) and age-class (aged ≤ 65 years versus > 65 years). The 95% confidence intervals will be provided for the risk difference.

Similar MH analyses and presentation of 95% confidence intervals will be applied to the main estimand of the first key secondary efficacy endpoint, which is defined as a binary variable indicating disease progression (death or respiratory failure) at Day 28, and the main estimand of the second key secondary efficacy endpoint that is defined as a binary variable indicating disease resolution (alive and have a score of 6, 7 or 8 on NIAID) at Day 28. Intercurrent events that lead to study drug discontinuation and/or switch to other treatment before Day 28 will be handled using the treatment-policy strategy for these 2 estimands (ie, the NIAID score at Day 28 will be used for definition of the failure or response, respectively) in such patients. Missing data on Day 28 will be imputed by multiple imputation using information from similar patients of the same treatment group. Missing postbaseline data for patients randomized but not treated will be imputed by BOCF.

A similar MH approach and presentation of 95% confidence intervals as described above will be applied also to the main estimand of the third key secondary efficacy endpoint, which is the all-cause mortality at Day 28. Intercurrent events that lead to study drug discontinuation and/or

This document is confidential.

Page 71 of 85
switch to other treatment before Day 28 will be handled using the treatment-policy strategy (ie, the life status at Day 28 will be considered). No missing data of life status on Day 28 is expected.

The main estimand of the fourth key secondary efficacy endpoint, change of clinical status related to COVID-19 on Day 28 compared with baseline according to the NIAID 8-point ordinal scale, will be compared using the risk difference from the analysis of covariance model with treatment and the 2 binary stratification factors (eg, severity and age-class) as independent factors and the baseline value of NIAID as independent covariate. Intercurrent events that lead to study drug discontinuation and/or switch to other treatment before Day 28 will be handled using the treatment-policy strategy for this estimand (ie, the NIAID score at Day 28 will be used). Missing data on Day 28 will be imputed by multiple imputation using information from similar patients of the same treatment group. Missing post-baseline data for patients randomized but not treated will be imputed by BOCF. The 95% confidence intervals will be provided for the risk difference.

The population for all above described estimands of the key secondary endpoints is the ITT.

Sensitivity analyses for the main estimands of the primary and key efficacy endpoints will be performed by assuming missing data at Day 14 or Day 28 as failure or non-resolution for the binary endpoints, and by multiple imputation using information from similar patients of the placebo group for the NIAID 8-point ordinal scale.

All above analyses for the main estimands of the primary efficacy and key secondary efficacy endpoints will be repeated on PPS as supportive analysis. Additionally, for the primary efficacy and binary key secondary efficacy endpoints, logistic regression model with treatment and the 2 stratification factors as covariables will be performed on the ITT. Further estimands for the primary and key secondary efficacy endpoints will be provided in the SAP.

The proportion of patients with disease resolution at Day 14 and the all-cause mortality rate at Day 14 and Day 60 will be analyzed using similar MH methods as described above for Day 28. Cumulative proportion of patients with disease resolution will be plotted by time.

A similar analysis of covariance approach as described above for Day 28 will be applied for the analysis of the change of clinical status related to COVID-19 on Day 14 compared with baseline on the NIAID 8-point ordinal scale. The endpoint considering the proportion of patients requiring invasive ventilation (mechanical ventilator and/or ECMO) or who are not alive, the proportion of patients in each NIAID category, and the proportion of patients alive and testing negative for COVID-19 on Day 14, Day 28, and Day 60, respectively, will be compared between the treatment groups using MH test. Overall survival, time to (first) improvement of at least 1 category on the NIAID scale and total hospitalization duration (from baseline to discharge; with death censored on last day of the observed period – at Day 28 or Day 60, respectively – depending on the analyses) will be summarized using the Kaplan-Meier method and will be compared between treatment groups using log-rank tests. Additionally, Cox proportional hazards model will be applied with treatment and the 2 stratification factors as covariables.

This document is confidential.

Page 72 of 85

Final

MetrioPharm AG MP1032	MP1032-CT05	
	Final	
MetrioPharm AG	MP1032-CT05	
MP1032	Protocol v2 0	

The odds ratio between MP1032 and SoC and placebo and SoC for the number of patients with clinical status improvement from baseline on the NIAID 8-point ordinal scale (ie, an improvement of at least 1 category) at Day 14 and Day 28 will be analyzed using a logistic regression with consideration of the 2 stratification factors.

The time to recovery of all at baseline present COVID-19 symptoms (stuffy or runny nose, sore throat, red or irritated eyes, shortness of breath, cough, low energy or tiredness, muscle or body aches, headache, chills or shivering, feeling hot or feverish, nausea, and number of times of vomit, times of diarrhea, sense of smell, sense of taste in the last 24 hours) will be presented by Kaplan-Meier estimates and figure. The change from baseline will be presented in shift tables for each single symptom, with the number and percentage of subjects in each category at post-baseline assessment time-point compared to baseline for each treatment group.

Total number of days in ICU, duration of invasive mechanical ventilation, and duration of ECMO will be descriptively summarized by treatment group using mean days with 90% confidence intervals and additionally by median days and quartiles. To consider death sufficiently unfavorable in these measures, in case of death, the duration of the respective measure will be considered with the longest duration possible (eg, if a summary of the first 28 days is presented, then death before Day 28 will be considered as duration 28 days, and if the summary also includes follow-up period until Day 60, then death before Day 60 will be considered as duration of 60 days). Both summaries (up to Day 28 and up to Day 60) will be provided.

For HRQoL assessments at discharge and Day 60, the EQ index value and the EQ VAS, both based on the EQ-5D-5L questionnaire (Appendix 2), will be calculated and summarized by visit and treatment group. Additionally, change at Day 60 from discharge will be summarized by treatment group.

All efficacy endpoints will be summarized using descriptive statistics by treatment group and by visit, as appropriate: Binary and categorical endpoints will be summarized by treatment group by presenting the number and percentage of patients in the categories. Continuous and ordinal endpoints will be described by mean, standard deviation, median, minimum, and maximum for actual values and change from baseline. Additionally, for ordinal data, the number and percentage of patients in each category will be presented.

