To standardize the assessment of COVID-19 severity, respiratory rate, SpO_2 , and heart rate will be measured when the patient is on room air at sea level (ie, no supplemental oxygen, if possible) and at rest for at least 5 minutes. If possible, the site should collect the information from each patient at the same time each day (± 1 hour).

Please note: Patients who are receiving oxygen therapy at baseline for a chronic condition (eg, emphysema, COPD, PAH, IPF, etc) must be considered as having severe COVID-19 (unless the patient meets the definition for critical COVID-19). For questions related to COVID-19 severity, the investigator should contact the medical monitor.

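### The primary endpoint is a cut between NIAID 4 and 5, but no planned binary analysis adjusts for the Day 1 NIAID score, which severity captures only in part

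*Protocol*

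**What the plan says.** - **Endpoint.** Protocol Sections 6.2 and 15.3 count death, or a NIAID score of 2, 3 or 4, as progression. Score 4 is hospitalised on supplemental oxygen. Score 5 is hospitalised without it and is not a failure. Day 28 progression uses the same cut. Day 28 resolution is a score of 6 to 8.
- **Primary analysis.** The population-level summary in Section 15.3 is "Common risk difference resulting from the Mantel-Haenszel (MH) test considering the 4 strata out of the combinations of the 2 randomization stratification factors". The same Mantel-Haenszel (MH) approach applies to Day 28 progression, resolution and mortality.
- **Supportive model.** For the same endpoints a "logistic regression model with treatment and the 2 stratification factors as covariables will be performed on the ITT".
- **Where baseline NIAID is used.** The analysis of covariance of NIAID change (Day 28, and Day 14 by reference) includes "the baseline value of NIAID as independent covariate", in addition to both stratification factors.
- **Severity.** Section 9.3.1 defines it by symptoms and signs: respiratory rate, heart rate, SpO2, PaO2/FiO2 or ARDS. Rates and SpO2 are taken off oxygen if possible. Oxygen support enters only through one rule: "Patients who are receiving oxygen therapy at baseline for a chronic condition" are classed as severe unless critical.
- **Availability.** The Schedule of Assessments (Table 1) records NIAID at screening and on Day 1.

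**The concern.** Inclusion criterion 3 requires hospital admission. Exclusion criterion 2 removes patients on invasive or non-invasive ventilation, ECMO, or high-flow oxygen above stated thresholds. Entry scores should therefore be mainly 4 or 5. A patient who enters at 4 already meets the endpoint's definition of respiratory failure and must improve to avoid being counted. A patient who enters at 5 must worsen to be counted. Baseline NIAID is thus likely to be a strong predictor of the outcome. For patients randomised but not treated, baseline observation carried forward makes an entry score of 4 a progression by rule.

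Severity separates these patients only in part. Someone can be severe on respiratory or heart rate without oxygen (score 5), or moderate while on acute oxygen with SpO2 above 93% and no other severe sign (score 4). With about 40 placebo patients, the arms can differ by chance in the share already on oxygen. Adjusting only after such an imbalance has been seen would be open to challenge.

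**Working it through.** **1. The plan's own figure.** Section 15.1 states: "Using the Chi-square test with type I error alpha=10% two-sided for this proof-of-concept study and 2:1 randomization ratio". It gives rates of 10% and 30%, and "114 randomized patients (76 in Arm A and 38 in Arm B) a statistical power of 83% can be achieved".

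- Pooled rate = (0.30 × 38 + 0.10 × 76)/114 = 19/114 = 0.1667.
- SE under the null = √[0.1667 × 0.8333 × (1/38 + 1/76)] = 0.0740.
- SE under the alternative = √[0.30 × 0.70/38 + 0.10 × 0.90/76] = 0.0819.
- Power = Φ[(0.20 − 1.645 × 0.0740)/0.0819] = 83.0%. This reproduces the stated figure, and 114/0.95 = 120.

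**2. MH with and without baseline NIAID.** The documents give neither the share entering at score 4 nor its prognostic strength, so both are assumed. Each scenario used 4,000 simulated trials with N = 120, stratified 2:1 blocks, and marginal rates of 30% versus 10%. The stratified (Cochran-Mantel-Haenszel) test over severity × age was compared with the same test over severity × age × NIAID (4 versus 5). Monte Carlo error is about 0.5 points.

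| Severe | Score 4 in moderate / severe | Odds ratio of score 4 | Power, planned | Power, with NIAID | Variance, planned ÷ adjusted | Arms differ by >10 points in share at 4 |
|---|---|---|---|---|---|---|
| 50% | 30% / 70% | 3 | 86.6% | 86.4% | 1.01 | 26% |
| 50% | 30% / 70% | 6 | 86.4% | 87.6% | 1.06 | 27% |
| 50% | 30% / 70% | 12 | 87.0% | 89.6% | 1.13 | 26% |
| 50% | 5% / 95% | 6 | 87.2% | 87.5% | 1.00 | 3% |
| 50% | 50% / 50% | 6 | 85.2% | 86.9% | 1.08 | 30% |
| 70% | 40% / 80% | 6 | 86.4% | 86.6% | 1.02 | 22% |
| 30% | 30% / 80% | 6 | 86.0% | 87.4% | 1.07 | 25% |

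The power change is −0.2 to +2.6 points. The largest variance ratio, 1.13, is a reduction of 1 − 1/1.13 = 11.5%. With no treatment effect the rejection rate is 10.4% versus 10.6% (odds ratio 6) and 9.6% versus 9.5% (odds ratio 12).

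**3. Standardised logistic model.** A steeper scenario assumes half the patients at score 4, control risks of 50% at score 4 and 10% at score 5 (overall 0.5 × 50% + 0.5 × 10% = 30%), relative risk 1/3, and severity agreeing with NIAID in 65%. Adding Day 1 NIAID to severity and age-class raises power from about 82% to 87%. In two milder scenarios the gain is 2 to 3 points. Type I error is about 11% with or without the adjustment.

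**4. Effect of a chance imbalance.** The SD of the between-arm difference in the share at score 4 is about 0.09. At 2:1 allocation, a difference of 0.09 puts Arm A 0.03 and Arm B 0.06 from the overall share.

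- Control gradient: 50% − 10% = 40 points.
- Treated gradient at relative risk 1/3: 16.7% − 3.3% = 13.3 points.
- Shift = 0.03 × 0.133 + 0.06 × 0.40 = 0.028, or about 3 points against a planned difference of 20.

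**The case against.** The strongest reply is that nothing here is an error. MH over the randomisation strata matches the stratified design, and chance imbalance is already part of the sampling variance that alpha controls. That stands. A reader might infer that the primary result is biased or the test invalid; the type I error results do not support this.

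A reader might also infer that severity says nothing about oxygen need. The protocol does not support that either. SpO2 of 93% or less off oxygen, PaO2/FiO2 below 300 and ARDS all make a patient severe, and the moderate class requires that no severe sign is present. Many patients given oxygen for desaturation should fall in the severe stratum. If severity almost determines the score (5% / 95%), the gain vanishes. The documents do not say how close the agreement is.

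A larger shift, 0.09 × 0.40 = 3.6 points, is tempting, but it applies the control gradient to both arms and so holds only if the drug has no effect.

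Adding NIAID as a further MH stratum is not the answer. Eight strata leave an average of 40/8 = 5 placebo patients each. About 0.10 × 80 + 0.30 × 40 = 20 primary events are expected, which limits how many covariates a model can carry. Day 28 deaths may be fewer still, and mortality is not a cut between 4 and 5.

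The SAP is not shown and may add estimands. The protocol itself, however, fixes the main summary and the logistic covariates. The planned covariance analyses do adjust for baseline NIAID, but for a different endpoint.

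**Conclusion.** The point holds as a question of efficiency and robustness. The variable most directly tied to the endpoint's cut is recorded on Day 1 and used as a covariate for the ordinal endpoint, but left out of every binary primary and key secondary analysis the protocol specifies. Over the scenarios tried, the cost is roughly 0 to 5 points of power, a planned variance 0 to 13% larger than the adjusted one, and a shift of about 3 points for a one-SD imbalance under the planned effect. When severity only partly tracks NIAID, the arms differ by more than 10 points in the share at score 4 in about 22 to 30% of trials.

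The omission is certain from the text. Its size is not, because the entry mix, the prognostic gradient and the agreement with severity are all assumed. The stated 83% power and N = 120 are unaffected.

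**What to change.** In Section 15.3, and in the matching synopsis text of each country version:

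- Add Day 1 NIAID (4 or lower versus 5 or higher) to severity and age-class in the logistic model for Day 14 progression, Day 28 progression and Day 28 resolution.
- Report the risk difference from that model by standardisation (g-computation) with a robust variance.
- Keep the four-stratum MH analysis alongside it, and state in advance which of the two is the main analysis.
- Do not use eight MH strata at N = 120.
- Do not require the extra covariate for Day 28 mortality if events are few.

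The cost is protocol and SAP wording plus programming. No new data are needed and the sample size does not change.
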